7.0 STATISTICAL CONSIDERATIONS

7.1 STUDY OUTCOME MEASURES

The primary objective of this study is to estimate the effect size in weight loss of supplementing the WW online program with gamified inhibitory control training (PolyRules!) among adults with overweight or obesity.

As a secondary objective, we will explore changes in dietary intake, physical activity, attention, inhibitory control and working memory over the course of study across study arms.

Primary endpoints

- Weight loss from baseline to 3 months.

Secondary endpoints

- As a secondary objective, we will explore dietary intake, physical activity, attention, inhibitory control and working memory over the course of the study and across study arms. We acknowledge that we are not powered to detect between-group difference on these outcomes. However, inasmuch as participants assigned to the WW only group do not engage in inhibitory control training, we expect no change in attention, inhibitory control and working memory over the course of the study among participants randomized to WW only.
- Qualitative outcomes measures will include participant's satisfaction with WW and PolyRules! (if applicable) and perceived benefits. Perceived satisfaction/dissatisfaction and preferred features of the WW and PolyRules! app will be qualitatively assessed and data obtained in semi-structured interviews will be summarized.

7.2 SAMPLE CONSIDERATIONS

- Sample size was defined based on available funding such that we expect drop-out over 3 months given the study is longitudinal. Therefore, a sample size of 30 will provide us a reasonable sample size to estimate the effect size.

7.3 STATISTICAL ANALYSES

Descriptive analysis will be presented with mean \pm standard deviation for quantitative variables, and frequency (percentages) for qualitative variables. A 95% confidence interval for the difference in weight loss between WW and WW + PolyRules! will be calculated. Cognitive test scores (inhibitory control, attention, verbal working memory tasks, visuo-spatial working memory tasks, and working memory capacity tasks), executive function, and physical activity questionnaires will be scored and summarized (Mean and SD) by group and used to inform the design of a larger randomized controlled trial. Calculations will be performed using R-package, version 4.0.⁵³

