4.0 STUDY DESIGN AND METHODS

4.1 OVERVIEW OF STUDY DESIGN AND PROCEDURES

Participants (n=30) will be randomly assigned to one of two arms: (1) WW (formerly weight watchers) only or (2) WW + Gamified inhibitory control training (PolyRules!). All participants will complete demographic, medical history questionnaires and cognitive assessment battery at baseline/enrollment and after completing the 3-month intervention protocol. As compensation for completing all study procedures, participants will receive a \$30 gift card.

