4.2 STUDY ARMS

WW (all participants; n = 30): All participants will receive pre-loaded computer tablets and 3-month access to the WW digital program. WW is a structured behavioral weight management program that focuses on diet, physical activity and mindset skills. The dietary approach is based on creating an energy deficit diet to produce weight loss while also being attentive to the quality of the calories. Specifically, the WW program assigns SmartPoints values to foods based on calories, sugar, saturated fat and protein. In addition, particular foods are assigned a points value of zero (0) to encourage a healthier eating pattern (e.g. fruits, vegetables, non-fat yogurt, fish). Upon sign-up, an individualized SmartPoints budget consisting of a daily SmartPoints target and weekly SmartPoints allowance is calculated based on height, weight, age and sex. The fitness component assigns FitPoints values to physical activities based on the type, duration, intensity and the participant's body weight. Participants receive 24/7 access to coaches, automatic enrollment in a rewards program based on behaviors, weekly emails motivating lifestyle changes and a closed social network for WW members.

WW + PolyRules! (50% of participants, n = 15): Participants assigned to the WW+ Polyrules arm will receive access to the WW online program (as described above) and to the PolyRules! app for three months. Participants will be trained on how to use PolyRules! via Zoom or Team Meeting platforms. Participants will be asked to engage in daily

cognitive training using the PolyRules! app for three months. They will be instructed to start with 20-min of daily cognitive training and to progressively increase their training time to 30-min. All interactions with PolyRules! will be passively recorded to monitor whether participants engage in cognitive training.

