4.3 MEASUREMENTS

Demographics

Participants will complete a questionnaire surveying: date of birth, sex, ethnicity, socioeconomic status (SES: education level, household income, marital status, employment status), household composition (multigenerational, single, married, cohabitating, children) and medical history.

Shared weight, dietary and physical activity data

As part of the WW experience, participants are instructed to track their weight, daily food intake and physical activity via the WW mobile app or online website. As a secondary objective, we will explore weight loss, dietary intake and physical activity over the course of the study and across study arms.

Cognitive Functioning

As a secondary objective, we will explore changes in attention, inhibitory control and working memory over the course of the study across study arms.

Executive Functioning

The Behavior Rating Inventory of Executive Function®- Adult Version (BRIEF-A) is a standardized measure of executive functions or self-regulation in everyday environment. The BRIEF-A assesses nine nonoverlapping theoretically and empirically derived clinical scales: Inhibit, Self-Monitor, Plan/Organize, Shift, Initiate, Task Monitor, Emotional Control, Working Memory, and Organization of Materials. BRIEF-A is available in English and Spanish and can be computer-administered.

Attention and Inhibitory Control Tasks

The *Cancellation Task* is a timed, tablet-based test of selective attention and inhibitory control, akin to D2 (Brickenkamp & Zilmer, 1998). There are two versions that can be used interchangeably: Cancellation Letters and Cancellation Pictures. Cancellation - Letters resembles the D2 in that it consists of similar stimuli: characters “d” and “p” with one to four dashes, arranged either individually or in pairs above or below the letters. For Letters, the participant must scan the items from left to right and select all “d”s with two dashes

(targets). In Cancellation - Pictures, letters are replaced with pictures of dogs and monkeys, some of which are rotated along the vertical axis or are presented upside down. For Pictures, the participant must select the upright dog (tail on the left) and the upside-down monkey (tail on right) separately in single blocks and together in a mixed block.

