8. Do you feel cognitive training helped you with your weight loss?		x
9. Can you tell me about some changes (good or bad) you have experienced since you have started using PolyRules!?		x
10. Would you continue using PolyRules! if available		x
11. Would you be interested in participating in a larger study testing the benefits of combining cognitive training and WW	x	x
12. Is there anything else you would like to share about the study	x	x

Schedule of Procedures

Procedures	Enrollment	Intervention	Post-Intervention
Informed Consent (DocuSign)	X		
Baseline assessment	X		
Randomization	X		
Equipment/software/application set-up and training		X	
Intervention: - WW only group - WW + PolyRules! group		X	
Post-intervention assessment			X
Exit interview			X
Equipment Return			X
Compensation			X

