5.2 TIME PERIOD OF DATA UNDER REVIEW

Questionnaire data will be collected at baseline / enrollment and after the 3-month intervention protocol. Frequency of PolyRules! use and interactions with the WW program will be passively recorded on the PolyRules! and WW platforms. Participant data will be included in the analysis if at least three valid days of interactions with the WW program and PolyRules! use (if applicable) are available. De-identified data will be kept for 5 years and then destroyed.

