5.3 VARIABLES COLLECTED

- Demographics: date of birth, sex, ethnicity, socioeconomic status (SES: education level, household income, marital status, employment status), household composition (multigenerational, single, married, cohabitating, children) and medical history

- **Weight, dietary and physical activity data.** Participants' reported/tracked weight, food intake and physical activity data via the WW mobile app or online website.
- Executive functioning as measured by the Behavior Rating Inventory of Executive Function® - Adult Version (BRIEF-A)
- Cognitive functioning: inhibitory control, attention, verbal working memory tasks, visuo-spatial working memory tasks, and working memory capacity tasks

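### Section 5.2's three-valid-days rule could remove randomised participants from the primary weight comparison, with an extra condition in one arm, and 7.3 has no drop-out handling: a modest, cheap improvement

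*Combined protocol and SAP*

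**What the plan says.** - **Endpoint and analysis.** Section 7.1 makes weight loss from baseline to 3 months the primary endpoint, and the objective is to estimate an effect size. For the comparison, 7.3 says "A 95% confidence interval for the difference in weight loss between WW and WW + PolyRules! will be calculated", after a general statement that quantitative variables are summarised by mean and SD. It names no analysis set, no window for the 3-month weight and no method for missing weights. No intention-to-treat statement appears anywhere.
- **Drop-out.** Section 7.2 says "we expect drop-out over 3 months given the study is longitudinal", with no rate and no handling.
- **Inclusion in the analysis.** Section 5.2 sets one condition on each person's data: "included in the analysis if at least three valid days of interactions with the WW program and PolyRules! use (if applicable) are available". A valid day is not defined, and the rule does not say which analysis it governs.
- **Source of weight.** Section 5.3 lists participants' "reported/tracked weight, food intake and physical activity data via the WW mobile app or online website". The schedule in 4.3 has a "Post-intervention assessment" but itemises no weigh-in. Section 4.1 describes what is done at the two time points: "All participants will complete demographic, medical history questionnaires and cognitive assessment battery at baseline/enrollment and after completing the 3-month intervention protocol". Section 4.3 also says "As a secondary objective, we will explore weight loss, dietary intake and physical activity over the course of the study and across study arms", so weights between baseline and month 3 are meant to be available.

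**The concern.** The PolyRules! part of the 5.2 rule can apply only to the WW + PolyRules! arm. If the rule is applied to weight loss, a person in that arm who tracked weight in WW but hardly opened PolyRules! is dropped, while the same kind of person in the WW-only arm stays. The comparison is then no longer between the groups as randomised.

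Drop-out adds a second selection. Weight is known only through self-tracking, so someone who stops tracking may have no month-3 weight. A difference among completers leaves that person out, although their earlier weights are on file. If those who leave had lost less, and more of them leave one arm, the estimate favours that arm. The effect size is the main product of this pilot, and 7.3 says that the results will inform a larger trial.

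**Working it through.** **Inputs from the documents.** 30 randomised (4.1), 15 of them to WW + PolyRules! (4.2), so 15 vs 15; endpoint and 95% interval as above. There is no plan figure to reproduce, because 7.2 bases the 30 on funding. The documents give no SD, mean loss, drop-out rate or tracking frequency. **Assumed throughout:** SD of 3-month change 3.5 kg, mean loss 4 kg. Positive values favour WW + PolyRules!.

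**Step 1: precision.** Half-width = t(0.975, n1+n2−2) × SD × √(1/n1 + 1/n2).
- 15 vs 15: 2.048 × 3.5 × 0.365 = 2.62 kg
- 12 vs 12: 0.847 × 3.5 = 2.96 kg
- 12 vs 10: 0.893 × 3.5 = 3.13 kg

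**Step 2: the 5.2 rule, if applied to weight.** Suppose k of 15 in the WW + PolyRules! arm are excluded and lost δ kg less than the other members of that arm. The full-arm mean is the retained mean minus kδ/15, so exclusion shifts the difference by kδ/15.
- k = 1: 1.75/15 = 0.12 kg; 3.5/15 = 0.23 kg
- k = 2: 3.5/15 = 0.23 kg; 7/15 = 0.47 kg

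The shift is zero if nobody fails the rule, and its sign reverses if those excluded lost more. As a cross-check, removing the least engaged share q of one arm gives a bias of ρ·φ(z_q)/(1−q) SD, where ρ is the correlation of engagement with loss. At q = 10% and ρ = 0.2 to 0.5 this is 0.039 to 0.097 SD, or 0.14 to 0.34 kg.

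**Step 3: drop-out.** Simulation with 15 per arm, one weight at each of months 0 to 3, baseline SD 12 kg and measurement error 0.7 kg. Drop-out occurs in the second and third months, and its log-odds fall by 1 per 3.5 kg more loss. Weight paths are linear, or half of the true change variance is a random walk. Completers: pooled t interval, 40,000 runs (Monte Carlo error 0.007 kg). Mixed model: 4,000 runs (0.02 kg). Bias in kg (linear; walk), with base hazards given as WW only vs WW + PolyRules!:

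| Drop-out | True benefit | Completers | Mixed model |
|---|---|---|---|
| Random, 24% per arm | 0 | 0.00; −0.01 | −0.01; +0.02 |
| Observed loss, 0.10 vs 0.10 | 0 | 0.00; +0.01 | −0.02; −0.03 |
| Observed loss, 0.07 vs 0.14 | 0 | +0.22; +0.21 | −0.01; −0.06 |
| Observed loss, 0.07 vs 0.20 | 0 | +0.42; +0.42 | 0.00; −0.04 |
| Observed loss, 0.20 vs 0.07 | 0 | −0.42; −0.42 | +0.02; +0.06 |
| Observed loss, 0.07 vs 0.20 | 1.75 | +0.30; +0.29 | 0.00; −0.03 |
| Unseen current weight, 0.07 vs 0.20 | 0 | +0.63; +0.59 | +0.12; +0.24 |

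For drop-out on observed loss, completers' intervals had half-widths of 2.9 to 3.1 kg and coverage of 94 to 95%; with unseen weight, coverage fell to 93%. A separately coded completer simulation agreed to within 0.03 kg. If drop-out follows an abrupt unseen regain (walk, 0.07 vs 0.20), the completer bias is +0.32 to +0.53 kg and the model still carries +0.25 to +0.46 kg. With 70% of the month-1 and month-2 weights missing, the model bias is +0.13 to +0.26 kg against +0.22 to +0.45 kg for completers.

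**Step 4: how the weights enter the model.** Step 3 used one weight per month, but tracked weights can fall on any date. With an assumed weekly weight, a true benefit of 1.75 kg, categorical months and a random slope in actual time, the bias was −1.34 kg (walk, coverage 75%) to −1.56 kg (linear, coverage 47%) in 400 runs per case (Monte Carlo error 0.04 to 0.06 kg). The fixed part has no within-month trend, so the random slopes absorb most of the effect. With all weekly weights and the slope on month number, the bias was −0.15 to −0.19 kg, because month 3 then averages earlier weeks. One weight per month gave about 0.

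**Step 5: sensitivity to drop-out not at random.** Let drop-outs have lost d kg less than predicted, with an assumed 3 (WW only) vs 5 (WW + PolyRules!) drop-outs of 15. For d = 1 to 3 kg the estimate
- falls by (5/15 − 3/15)d = 0.13 to 0.40 kg (both arms);
- falls by (5/15)d = 0.33 to 1.00 kg (WW + PolyRules! only);
- rises by (3/15)d = 0.20 to 0.60 kg (WW only).

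**The case against.** The best defence is that little is at stake. The 5.2 rule follows a sentence on passively recorded use and may be meant for usage data alone. Three days in three months is a low bar, and section 1.0 reports that all ten pilot users completed ten days of training, so perhaps nobody would fail it. Mean and SD followed by an interval for the difference ordinarily means a difference in mean change, so an estimator is implied. The trial is a pilot sized by funding. A mixed model can also do harm if badly specified (step 4), and the simulated gain is helped by letting everyone supply a month-1 weight.

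Most of this stands. It limits the size of the point and dictates how the model must be worded. It does not remove the gap: the 5.2 wording is unqualified, no other section corrects it, and two analysts following the plan could analyse different people.

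A reader might go further and infer any of the following; the documents do not support them.
- **The plan commits to an unequal exclusion from the primary comparison.** The scope of the rule is unstated, so this is one reading.
- **The bias favours PolyRules!.** Section 4.2 adds a daily burden in that arm ("They will be instructed to start with 20-min of daily cognitive training and to progressively increase their training time to 30-min"), which might raise drop-out there, but the complete adherence of the pilot users points the other way.
- **No primary estimator exists, or the interval would be invalid.** A difference in means is implied, and simulated coverage hardly moved.

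**Conclusion.** The point holds as a modest, optional-grade improvement. The text establishes three things: an analysis-inclusion rule of unstated scope with an added condition in one arm, expected drop-out with no handling, and weights known only through self-tracking.

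The size rests wholly on assumed inputs. It is about 0.1 to 0.5 kg (roughly 0.03 to 0.13 SD) if 1 or 2 of 15 are excluded, or if drop-out differs by arm and follows observed poor loss. It reaches about 0.6 kg if drop-out follows the unseen current weight. It is zero if nobody fails the rule and drop-out is random. Against a half-width of about 3 kg this is small, and either sign is possible. The reason to act is the low cost and the use of the estimate in planning a larger trial.

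**What to change.** 1. **Section 5.2.** Limit the three-valid-days rule to usage summaries or a supportive analysis, and state that it excludes no randomised participant from the primary weight comparison.
2. **Section 7.3, with the windows stated there or in 7.1.** Estimate the month-3 difference and its 95% interval from a linear mixed model of all randomised participants. Use one weight per person per pre-stated monthly window: the tracked weight nearest months 0, 1, 2 and 3. Specify a common baseline mean, arm-by-month terms, a random intercept, a random slope on nominal month, and REML. Do not enter all tracked weights on their actual dates with categorical months and a random slope in actual time. Report the completer difference beside it in every case, labelled as such, so that no undefined sparsity criterion decides the estimator after the data are seen.
3. **Sensitivity.** Add one analysis in which drop-outs lost a pre-stated amount less than predicted, in both arms and then in one arm only.

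**Cost.** Wording in 5.2, 7.1 and 7.3 and a few lines of R; no new participants or visits.

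**Downside.** The model assumes missing at random with 30 people. It removes little bias if people stop tracking after an unrecorded regain or if interim weights are sparse, and it gains almost nothing from someone with no weight after baseline. The sensitivity analysis is there for these cases.

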2.0 STUDY OBJECTIVES

2.1 Primary objective: To estimate the effect size in weight loss of supplementing the WW (formerly Weight Watchers) online program with gamified inhibitory control training (PolyRules!) among adults with overweight or obesity.

2.2 Secondary objectives: To explore whether inhibitory control training confers any benefits in terms of diet quality, physical activity or cognitive functioning in the early stages of a weight management program.

[figure not shown]

Fig 2. Improved inhibitory control over 10-day training.

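### Section 7.3 plans only group means and SDs for cognition, although the secondary aim concerns change across arms; a baseline-adjusted difference with a 95% CI would answer it from data already collected

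*Combined protocol and SAP*

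**What the plan says.** The secondary objective in section 2.2 is "To explore whether inhibitory control training confers any benefits in terms of diet quality, physical activity or cognitive functioning". Section 4.3 puts the cognitive part in terms of change: "we will explore changes in attention, inhibitory control and working memory over the course of the study across study arms". Section 7.1 repeats this for the secondary outcomes and adds a caution: "We acknowledge that we are not powered to detect between-group difference on these outcomes".

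The data needed are collected in both arms. Under section 4.1 all participants complete the "cognitive assessment battery at baseline/enrollment and after completing the 3-month intervention protocol".

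The analysis is in section 7.3. For the primary endpoint, "A 95% confidence interval for the difference in weight loss between WW and WW + PolyRules! will be calculated". Cognitive scores and executive function "will be scored and summarized (Mean and SD) by group and used to inform the design of a larger randomized controlled trial". No visit, change score, between-arm difference or interval is named for them.

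Two other sections affect who would be compared. Section 7.2 says "we expect drop-out over 3 months given the study is longitudinal". Section 5.2 has a general inclusion rule: "Participant data will be included in the analysis if at least three valid days of interactions with the WW program and PolyRules! use" are available, with the PolyRules! part required only where it applies, which is in one arm.

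**The concern.** In a two-arm randomised study, asking whether training benefits cognition is asking for a difference between arms. Section 7.3 gives the reader two columns of means and SDs and leaves that difference to be worked out.

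How much can be worked out depends on what is tabulated, and section 7.3 does not say:

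- Visit-level summaries give a crude 3-month difference with its interval. They also give the point estimate of the difference in change if the same people contribute to both visits. They do not give the interval for that difference, because the baseline-to-3-month correlation is missing.
- Change summaries give the difference in change and its interval.
- Neither table on its own gives the baseline-adjusted difference.

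The missing correlation also bears on the stated purpose of informing a larger trial, since the SD of change and the gain from baseline adjustment both depend on it.

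**Working it through.** **Figure in the plan.** The sample is 30, with 15 in WW + PolyRules! (sections 4.1 and 4.2) and therefore 15 in WW only. Section 7.2 bases it on funding. No power, precision, SD or effect size is given for cognition, so there is no figure to reproduce. What can be checked is what the added estimate would buy at that size.

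**Inputs.** n = 15 per arm is from the plan. Drop-out is expected but no rate is given, so 12 per arm is an assumed case. The correlation r between baseline and 3-month scores is not in the documents and is assumed at 0.3, 0.5, 0.7 and 0.8. Scores are taken as roughly normal with the same SD at both visits, and half-widths are in units of that SD.

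**Formulas for the 95% CI half-width.**

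- Unadjusted 3-month difference: t(0.975, 2n−2) × √(2/n)
- Difference in change: the same × √(2(1−r))
- Baseline-adjusted difference (ANCOVA): t(0.975, 2n−3) × √(1−r²) × √(2/n) × √(1 + 1/(2n−4)), where the last factor allows for chance baseline imbalance

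**At n = 15.** √(2/15) = 0.365. The unadjusted 3-month half-width is 2.048 × 0.365 = 0.748. The ANCOVA multiplier is 2.052 × 0.365 × √(1 + 1/26) = 0.763, to be multiplied by √(1−r²).

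| r | Difference in change | Baseline-adjusted | Narrower than change by |
|---|---|---|---|
| 0.3 | 0.748 × 1.183 = 0.885 | 0.763 × 0.954 = 0.728 | 18% |
| 0.5 | 0.748 × 1.000 = 0.748 | 0.763 × 0.866 = 0.661 | 12% |
| 0.7 | 0.748 × 0.775 = 0.579 | 0.763 × 0.714 = 0.545 | 6% |
| 0.8 | 0.748 × 0.632 = 0.473 | 0.763 × 0.600 = 0.458 | 3% |

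A simulation under the same assumptions gave mean ANCOVA half-widths of 0.722, 0.655, 0.539 and 0.454, within 0.01 of these, with coverage of 0.948 to 0.952.

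**At n = 12.** The unadjusted 3-month half-width is 2.074 × 0.408 = 0.847. For r = 0.3, 0.5, 0.7 and 0.8, the difference in change has 1.002, 0.847, 0.656 and 0.535. The ANCOVA multiplier is 2.080 × 0.408 × √(1 + 1/20) = 0.870, which gives 0.830, 0.753, 0.621 and 0.522.

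**Against the unadjusted 3-month difference (0.748 at n = 15).** ANCOVA is 3%, 12%, 27% and 39% narrower at r = 0.3, 0.5, 0.7 and 0.8. At r = 0 it is 2% wider (0.763).

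**In participants, at r = 0.7.** A difference in change needs about 17 per arm to match ANCOVA with 15: at n = 17, t(0.975, 32) × √(0.6 × 2/17) = 2.037 × 0.266 = 0.541.

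**Chance exclusions.** With six 95% intervals and no true effect, 6 × 0.05 = 0.3 would be expected to exclude zero.

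**The case against.** The strongest reply is that the plan has a coherent hierarchy: estimate the primary outcome with an interval and describe the rest. The secondary aim is worded as exploration, the lack of power is stated openly, and N was set by funding. Nothing planned for cognition is biased or invalid. This stands, and it is why the point is an improvement and not an error. It does not remove the value of an interval. Low power is a reason not to lean on significance tests, whereas an interval shows how little or how much the data say.

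A second reply is that the gain is modest against the right comparator, and this also stands. A reader might infer that adjustment is worth nearly doubling the sample, because at r = 0.7 it matches an unadjusted 3-month comparison with about 28 per arm. Sections 4.3 and 7.1 speak of change, however, and against the difference in change the equivalent is about 17. Nor can the planned table be said to leave the reader with the least precise answer. Section 7.3 does not say what is tabulated, and when r is below 0.5 the difference in change is less precise than the crude 3-month difference.

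A reader might also infer that the plan never says whose data are analysed. Section 5.2 does give a general rule. What remains open is how missing 3-month scores are handled and whether a rule requiring PolyRules! use in one arm only suits this comparison.

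Finally, reaction times and threshold scores may not be normal, so the half-widths are illustrative.

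**Conclusion.** The point holds as a gap in estimation, worth correcting because the correction is cheap. The plan asks a between-arm question about cognitive change and provides no between-arm estimate or interval for it. The baseline-adjusted estimate is no wider than the difference in change at any correlation examined. Its advantage is largest at low correlation (18% at r = 0.3) and small at high correlation (3% at r = 0.8). Against the crude 3-month difference the pattern reverses, with little gain at r = 0.3 and a large one at r = 0.8. Not having to know in advance which simpler contrast would do better is the practical argument for it.

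These sizes rest on an assumed r, equal SDs and approximate normality, none of which the documents supply. They do not show that descriptive reporting is wrong or that any stated figure is in error.

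**What to change.** In section 7.3:

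1. Name in advance one score for each of the five cognitive tasks (Cancellation, Countermapping, N-Back, Letter-Number, Corsi) and one BRIEF-A score, six in all.
2. For each, report the between-arm difference at 3 months adjusted for the baseline score, with a 95% CI, in participants with both visits, analysed as randomised. Label it exploratory and unadjusted for multiplicity.
3. Alongside, give n, mean and SD at each visit and of change, by arm, and the baseline-to-3-month correlation.
4. Do not apply the three-valid-days rule of section 5.2 to this comparison, or show the result under it as a sensitivity analysis, because it filters on PolyRules! use in one arm only.

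The cost is a few lines of plan text and R code, with no new visits or participants. The downside is six wide intervals, which must be presented as showing the limits of the data. Showing the section 5.2 version as well would add six more.
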